Nutrition assessment surveys are most commonly cross-sectional descriptive surveys used to estimate the prevalence rates of various types of malnutrition. Surveys can also assess the role of risk factors and identify vulnerable subgroups. Surveys will often be carried out in many different situations and populations, such as 1) in refugee camps or camps for internally-displaced persons which are organized and run by local government authorities or international organizations; 2) in displaced populations which are integrated into a local host population; and 3) in emergency-affected populations which are not displaced. Surveys in non-displaced populations are similar to those done in stable populations not affected by emergencies.

Objectives

The objectives of nutrition assessment surveys in emergency-affected populations usually include at least some of the following:

- 1) Estimate the current prevalence of acute malnutrition (wasting) and chronic malnutrition (stunting) among children 6-59 months of age.
- 2) Estimate the current prevalence of protein-energy malnutrition among women of childbearing age (15-49 years of age).
- 3) Estimate the current prevalence and severity of anemia among children 6-59 months of age, women of child-bearing age, and possibly adult men age.
- 4) Estimate the current prevalence and severity of vitamin A deficiency among children 6-59 months of age and women of child-bearing age.
- 5) Estimate the current prevalence and severity of other micronutrient deficiencies in various target population groups. Such deficiencies and target groups may include iodine deficiency in children 8-11 years of age; B vitamin deficiency in children, adolescents, or adults; vitamin D deficiency in children 6-59 months of age; or others.
- 6) Estimate current household food consumption patterns, household food security, and food consumption in children 6-59 months of age.
- 7) Estimate the measles immunization coverage among children 9-59 months of age.
- 8) Estimate the cumulative 2-week prevalence of diarrheal disease and acute lower respiratory infection in children 6-59 months of age.
- 9) Estimate the crude mortality rate and age-specific mortality rate for children less than 5 years of age.

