Measles immunization coverage. Measles immunization status is most often determined by asking an adult caretaker, preferably the mother, if the child has ever been vaccinated against measles. In some populations where mothers have written health records, such as vaccination cards, evidence of measles vaccination will consist of a written record of immunization. In other populations where vaccination cards are not widely available, the mother's verbal report will serve as evidence of vaccination.

Cumulative prevalence of diarrhea and acute lower respiratory infection. During interviews with an adult caretaker, survey workers define diarrhea as 3 or more bowel movements in the prior 24 hours. The child's having had diarrhea at any time in the prior 2 weeks is considered positive. Acute lower respiratory infection is defined as the presence of cough and fever; having this condition at any time in the prior 2 weeks is considered positive.

Participant inclusion criteria

Households are eligible for participation in nutrition assessment surveys if they fit the clearly defined criteria established before sampling takes place. Such criteria are most often geographic because most surveys are done to estimate nutritional status in a geographically defined emergency-affected population or the population of a specific camp. Individuals in selected households are eligible for participation if: 1) they fit the criteria defining a target subgroup, such as children 6-59 months of age, women of child-bearing age, etc. 2) they live in a selected household at the time of data collection, and 3) consent is given by the participant or a responsible adult for survey participation.

Participant exclusion criteria

Households will be ineligible for participation in nutrition assessment surveys if 1) they are empty, that is, if no one from the household currently lives in the defined population, or 2) consent for participation is denied by the adult household member approached by the survey team. Individuals in selected households will be ineligible if consent is denied.

Justification of exclusion of any sub-segment of the population

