No sub-segment of the population will be specifically excluded from participation in nutrition assessment surveys in emergency-affected populations; however, some population subsegments may not be specifically chosen for inclusion. Women and children are at greater risk of most nutritional deficiencies; therefore, they will be targeted for most nutrition assessment surveys. Men are at substantially lower risk of many nutritional deficiencies and are therefore specifically not targeted for most nutritional assessments. One exception is the assessment of the causes of anemia. Men are often included in such surveys because they are much less susceptible to iron deficiency. Therefore, survey findings indicating that anemia is common among women and children but rare among men provide evidence that iron deficiency is a predominant cause of anemia.

Estimated number of participants

The specific sample size in each nutrition assessment survey depends on many assumptions and factors which may differ from one survey to the next. Commonly, such surveys include 200 - 700 households and all eligible members of target groups who live therein.

Sampling, including sample size and statistical power

The required sample size will be calculated separately for each assessment survey. All sample size calculations use the following assumptions:

- 1) The limit of statistical significance (alpha) = 0.05
- 2) The power (beta) = 0.8

The other assumptions required for sample size calculation will be decided based on the specific population to be assessed. These assumptions include:

- 1) Prevalence of nutritional condition of interest
- 2) Desired precision of point estimate of prevalence, cumulative prevalence, incidence, or mean.
- 3) Population size, if less than 10,000.
- 4) Design effect, if cluster sampling is planned.

The table below shows examples of nutrition conditions of interest, the assumptions used, and the sample size needed which may be used in nutrition assessment surveys in emergency-affected populations. These examples assume a population size greater than 10,000. Of course, the assumptions used and therefore the required sample sizes will differ depending on the nutrition conditions and specific population to be assessed.

Target group and type of malnutrition	Assumed current value	Precision required	DEFF assumed	Sample size needed
Children 6-59 months				
Wasting (< -2 SD)	20%	" 5%	2	492
Stunting (< -2 SD)	50%	" 10%	2	193

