The entire data collection form, including interview questions, is translated into the language or languages spoken by survey team members and survey participants by native speakers of these languages. The translation is then back translated into English by different translators. Differences between the original and back-translated English forms are resolved by the two translators working with the survey supervisor. Interview questions are read verbatim by interviewers during data collection. An example of the English version of such a data collection form is given in Appendix 1.

Interviews. Interviews will be conducted by appropriate survey team members who have received instruction in the type of data to be collected by each specific question and the reason these data are being collected. Interview questions will be read verbatim from the interview form. Interviewees will be allowed to refuse answers to any or all of the questions.

Anthropometric measurements. All anthropometric measurements, most commonly consisting of height, length, weight, and MUAC, will be taken using standard methods. For example, for children 6-59 months of age, all measurements will be taken using the procedures outlined in the UNICEF training manual "How to Weight and Measure Children.." All anthropometric indices will be calculated using either the NCHS/CDC/WHO reference population, or if available, the new WHO reference population. Anthropometric measurements on adults are less standardized. Weight will be measured with a properly calibrated bathroom-type scale. Height will be measured using a portable stadiometer while the subject stands against a vertical surface. For other target groups, including adolescents, methods may differ depending on current knowledge.

Physical examination. In some nutrition assessment surveys, collection of biologic specimens may be infeasible or ill advised. In such cases, survey subjects may be examined for signs or symptoms of specific micronutrient deficiencies. In all cases where protein-energy

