created when the final selection of households or individuals is made during the sampling process. In cluster surveys, there is a separate form for each cluster, often called a cluster control form, which lists all the households or individuals selected for that cluster. These sample lists and cluster control forms will contain both identifying information and the numeric code described above, and thus can serve as a key to match the code numbers to specific individual participants. This key is necessary to follow-up with specific survey participants if necessary. At the end of the survey, these sample lists will be destroyed or permanently stored separate from the paper data collection forms. Only authorized survey coordinators will have access to the sample lists and data collection forms. Final deposition of all paper and electronic survey materials, including computer datasets and paper forms, will be determined by the organization or agency which funds the survey. In most cases, the sample lists and paper data collection will not return to Atlanta with IERHB personnel.

APPENDIX 1

Nutrition and Health Survey, Afghanistan, 2002

Province	District	Village)	
Cluster number:	_Household number:			
Team code:	Interviewer code:	Date of interview:	/	
			Day	Month

HOUSEHOLD DATA

1)	Does your family now live in your usual place of residence? (circle one)	Yes	/ N o / U nk
	1a) If NO, how long since the family has lived there?	months OR	years
2)	Has anyone in the family received any relief food since the change in government?.	Yes /	No / Unk
3)	What is your main source of water? (circle one)Central piped system /	Truck or water seller	r / Bore hole
	Open W ell / R iver	or stream / Lake or p	ond / Other
4)	Do you use the same source of water now as you did this time last year?	Yes /	No / Unk
5)	How long does it take you to fetch water each time you go to get it?	······	minutes
6)	Results of iodine testing of salt used for last night's food (circle one)I	Positive / Negative	/ Not Done

I would like to ask you about each person who **lived in this household at the time of Eid Qurban 1379** (2001 Gregorian calendar) and children who were born since the time of Eid Qurban:

HOUS Head of on	EHOL house 1 st line	D MEMBI	ERS 1. 2. 3. 4.	Alive (livin Alive (livin Died Missing/L	ng in this ho ng elsewho Jnknown	ousehold) ere)	When was he/she did he/she h feet or leas	became ill, very thin or nave swollen	was she pregnant or at the time of Chil or Nefaz?

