9) H	Has this child recei (show example)	ved any vitar	in A? Vitamin A is given as	drops fron	n a capsi	ule	Yes	N o	/	U nk
10)	Since 2 weeks ago	o, has this chi	d had diarrhea? Diarrhea is	3 or more	e stools i	n 24 hours	.Yes	/ N o	/	Unk
	10a) If YES, was	s this child tak	en to a clinic or hospital for	this proble	em?		.Yes	/ N o	/	Unk
11)	Since two weeks a	ago, has this c	hild had fever and difficulty	breathing	·		.Yes	/ N o	/	Unk
	10a) If YES, was	s this child tak	en to a clinic or hospital for	this proble	em?		.Yes	/ N o	/	Unk
12)	Since the change This vaccine is g	of governmen given by inject	t, has this child received me ion.	asles vac	cination?		.Yes	/ N o	/	U nk
Exa	mination of child									
13)	Bitot's spots							Yes	/	No
14)	Gums bleeding sp	ontaneously.						Yes	/	Νο
15)	Gums bleed upon	tapping						Yes	/	Νο
16)	Angular stomatitis						······	Yes	/	Νο
17)	Pallor in palms of I	hands						Yes	/	No
18)	BCG scar							Yes	/	No
19)	Row of ricketts							Yes	/	No
20)	Perifollicular hemo	orrhage						Yes	/	No
21)	Swollen joints – so	oft and painful						Yes	/	Νο
22)	Swollen joints – ha	ard and not pa	inful					Yes	/	Νο
23)	Bruises or eccymo	sis on legs						Yes	/	No
24)	Bowed legs							Yes	/	No
25)	Bilateral edema							Yes	/	No
26)	Spinal deformity							Yes	/	No
27)	Does this child hav	ve a physical	deformity making it difficult to	o obtain a	n accura	te height?		Yes	/	No
Anth	propometry and lat	poratory								
28)	Weight: (kgs)							,	·	
29)	Length/Height: (cn	ns)						,		
30)	MUAC: (cms)									
31)	Hemoglobin:

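### The protocol takes measles status as ever vaccinated, but its example form asks only about doses since a political event, so using that item for objective 7 could understate coverage

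*Protocol*

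**What the plan says.** Three places in the Protocol bear on this.

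- **Objectives, item 7:** "Estimate the measles immunization coverage among children 9-59 months of age". No period is attached to the dose.
- **Case definitions, measles immunization coverage:** "Measles immunization status is most often determined by asking an adult caretaker", and the question put to the caretaker is "if the child has ever been vaccinated against measles". A written record serves as evidence where cards are in use, and the mother's report where they are not. Again there is no period.
- **Appendix 1, child form, item 12:** the item opens with "Since the change" of government and asks whether the child has received measles vaccination, answered yes, no or unknown. The form as shown has no other measles item; the BCG scar item concerns a different vaccine.

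The Data collection section describes the form's status: "An example of the English version of such a data collection form is given in Appendix 1". Its title is "Nutrition and Health Survey, Afghanistan, 2002".

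**The concern.** The case definition and the form measure different things. The first is lifetime vaccination status; the second is vaccination within a window that opens at a political event. Anyone adapting the example form would have to replace the event with a local one, and could carry the window forward without noticing that it no longer matches the definition.

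At stake is whether objective 7 reports what it names. Under the section on disseminating results, a vaccination coverage estimate is among the figures in the rapid preliminary report discussed with the participating organizations. Recent uptake presented under the name of coverage would misinform those readers.

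**Working it through.** The Protocol states no measles coverage, precision or sample size, and its sample-size table has no measles row. There is therefore no figure to reproduce. The check compares texts and then follows the logic.

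**Side by side**

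| Child's history | Under the case definition | Under item 12 |
|---|---|---|
| Dose since the event, with or without an earlier one | Vaccinated | Yes |
| Dose only before the event | Vaccinated | No |
| No dose | Not vaccinated | No |

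The two disagree only in the second row.

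**Direction.** Among children 9-59 months let

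- s = share with a dose since the event (what item 12 measures),
- b = share with a dose before the event,
- o = share with a dose only before the event.

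Ever-coverage = s + o, so the shortfall is (s + o) − s = o, which is never negative. Doses since the event are a subset of doses ever received, so the window can leave the estimate equal to ever-coverage or below it, never above.

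**Limits on size.** Given b and s, the shortfall lies between max(b, s) − s and min(1, b + s) − s. If earlier and later vaccination are independent it equals b(1 − s). It is zero if no child was vaccinated before the event, or if every child vaccinated before was vaccinated again since.

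**How far this leaves the size open.** The values of b and s below are assumed and are not in the documents. They show how the formula behaves and are not evidence of the actual shortfall.

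- b = 10%, s = 80%: under independence 0.10 × 0.20 = 2 points; limits 0.80 − 0.80 = 0 and 0.90 − 0.80 = 10 points.
- b = 50%, s = 40%: under independence 0.50 × 0.60 = 30 points; limits 0.50 − 0.40 = 10 and 0.90 − 0.40 = 50 points.

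**Would the plan's checks find it?** Back-translation compares the translated form with the English original, the team leader's review looks for completeness and accuracy, and the data-entry check compares paper with computer file. Each would faithfully preserve the window. The 95% confidence limits describe sampling error around s, so they would not show the gap either.

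**The case against.** The strongest reply is that the form only illustrates. The Protocol calls it an example, its wording is tied to one country and year, and the general variable list names measles vaccination with no window. The case definition says the ever-vaccinated question is used most often, not always, and the objectives are a menu from which each survey chooses. Household question 2 on the same form uses the same event for relief food, so that survey may have wanted a period measure. Most of this stands, and it limits the point to what happens if the item is used for objective 7. It does not remove the mismatch, because the Protocol neither says that item 12 is a period measure nor defines one for measles.

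A reader might infer several stronger things that the documents do not support:

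- **That every survey under this Protocol understates coverage.** An example form from one survey cannot show that, and no text says item 12 alone feeds objective 7.
- **That the wording cannot be repaired in the field.** Questions are read verbatim, but the training section has interviewers help pretest and revise them beforehand. That step is aimed at clear and culturally fitting wording, so it may miss this mismatch, but it does allow a correction.
- **That the form wrongly lacks a card field.** The case definition accepts the mother's report where cards are scarce, and a form without that field is consistent with this.
- **That the error would trigger needless mass vaccination.** The interventions the Protocol lists concern food, feeding and micronutrients.

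**Conclusion.** The inconsistency is real: the only instrument supplied cannot, as worded, recover the variable that the case definition and objective 7 describe. If item 12 or an adapted event-bound version is used for objective 7, coverage is understated by the share of children vaccinated only before the event. The direction is certain on that condition and assumes truthful answers.

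The size cannot be derived from the documents and may be zero. The conclusion concerns the example item and its reuse; it is not a finding of bias in any particular survey. It is worth correcting because the error would be a bias that a larger sample does not reduce.

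**What to change.** Either of two changes resolves it.

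1. Reword item 12 to ask whether the child has ever received measles vaccination, and compute objective 7 from that answer in children 9-59 months. If recent uptake is also of interest, add an optional follow-up for those answering yes: was a dose given since [local event]?
2. Keep item 12 as it is, label it as uptake since the named event, and state that it is not to be reported as measles coverage. A survey that includes objective 7 would then need a separate question on ever having been vaccinated.

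The first is simpler. It costs one reworded question and, if wanted, one short follow-up. Sampling, sample size and the other items are unaffected.

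### Diarrhea is defined by stool count alone, so the 2-week prevalence may be biased upward by an unknown amount; the definition's 24-hour wording also conflicts with its 2-week window

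*Protocol*

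**What the plan says.** Objective 8 in the Protocol's Objectives is: "Estimate the cumulative 2-week prevalence of diarrheal disease and acute lower respiratory infection in children 6-59 months of age".

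The general definition stands under Case definitions, in the paragraph on cumulative prevalence of diarrhea and acute lower respiratory infection: "survey workers define diarrhea as 3 or more bowel movements in the prior 24 hours". The next sentence sets the window: "The child's having had diarrhea at any time in the prior 2 weeks is considered positive".

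In Appendix 1 (the 2002 Afghanistan form), question 10 asks whether, since two weeks ago, the child has "had diarrhea? Diarrhea is" and completes the gloss with three or more stools in 24 hours. Neither place mentions stool consistency or a change from the child's usual pattern, and no other section adds such a criterion.

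Under Data collection: "Interview questions will be read verbatim from the interview form". The same section presents Appendix 1 as an example of a form. Training for all study personnel says that interviewers help to pretest and revise the questions.

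**The concern.** The objective concerns diarrheal disease, but the rule measures bowel frequency. A healthy child with three formed stools on any one day of the two weeks satisfies the count. The target group starts at 6 months, and question 6 of the form shows that breastfed children are expected, so frequent normal stools are a realistic possibility in part of the sample. Any resulting error would probably be largest in the youngest children.

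Three things make this more than a matter of style:

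- Stool consistency is never asked, so no later analysis can recover it.
- Faithful translation and back-translation preserve the gap.
- The clinic-attendance follow-up to question 10 is asked only after a yes. Healthy children answered as cases would enter its denominator and could make care-seeking look lower than it is.

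The time wording is a second fault in the same sentence. The Case definitions count stools over the last 24 hours but call a child positive for any time in two weeks.

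**Working it through.** **Comparing the texts**

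| Element | Case definitions | Appendix 1, question 10 |
|---|---|---|
| Count | 3 or more bowel movements | 3 or more stools |
| Consistency | none | none |
| Period for the count | the last 24 hours | 24 hours, not tied to the last day |
| Window for a positive child | any time in the past 2 weeks | since 2 weeks ago |

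The first two rows show that the lack of a consistency term is common to both places. The third shows that the two differ on the period for the count. Within the Case definitions, the third and fourth rows cannot both be applied literally.

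**Is there a figure to reproduce?** No. The Protocol gives no diarrhea prevalence, precision or sample size. What follows shows direction and scale only.

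**Effect of the missing consistency term**

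Let p be the true 2-week prevalence, and f the share of children without diarrhea who had a day with three or more normal stools and are answered yes. Neither is in the documents; both are assumed. Assume also that every true case meets the count. Then

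recorded = p + (1 − p) × f.

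| p | f = 2% | f = 5% | f = 10% | f = 20% |
|---|---|---|---|---|
| 10% | 11.8% | 14.5% | 19.0% | 28.0% |
| 20% | 21.6% | 24.0% | 28.0% | 36.0% |
| 30% | 31.4% | 33.5% | 37.0% | 44.0% |

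For example, at p = 20% and f = 5%: 0.20 + 0.80 × 0.05 = 0.24.

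A narrower model confines the error to ages 6-23 months. With an even age spread these are 18/54 = one third of the target group, and

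recorded = p + (1/3) × (1 − p) × f.

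With f from 5% to 30% in that third, p = 20% is recorded as 21.3% to 28.0%, and p = 30% as 31.2% to 37.0%. At f = 5% and p = 20% the two models give 24.0% and 21.3%. The documents cannot choose between them.

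**Scale against sampling error**

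The wasting row of the sample size table (20%, ±5%, design effect 2) reproduces: 2 × 1.96² × 0.20 × 0.80 / 0.05² = 491.7, printed as 492. If diarrhea were also at 20% with n = 492 and design effect 2, the 95% half-width would be 1.96 × √(2 × 0.20 × 0.80 / 492) = 5.0 points. Bias exceeds this when f is above 0.05/0.80 = 6.25% in the first model, or above 0.05/(0.80/3) = 18.75% in the narrower one. Below those values it lies within sampling error, although a larger sample would not shrink it.

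**Effect of the 24-hour wording, read literally**

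Let s be the share of true 2-week cases that meet the count in the last 24 hours, and g the share of children without diarrhea who meet it in that one day. Then

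recorded = p × s + (1 − p) × g.

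This is below p whenever g < p(1 − s)/(1 − p); at p = 20%, whenever g < 0.25 × (1 − s). Neither s nor g is in the documents, so under the literal reading the net direction is not fixed.

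**The case against.** The strongest objection is that the caretaker is asked whether the child had diarrhea, with the count following as a gloss. A caretaker who does not regard normal stools as diarrhea can answer no. This stands: f may be small. The screening is uncontrolled, however, and the stated gloss invites a count.

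Second, the form is one survey's example, open to revision after pretesting. This stands for question 10. It does not cure the Case definitions, which are general and have the same gap.

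Third, the stakes are limited. Surveys take up only some of the listed objectives, the final sample size is often set on nutrition outcomes in young children, and none of the interventions listed under Anticipated products depends on diarrhea prevalence. Subgroup tests are mentioned only in general terms, and no diarrhea comparison by breastfeeding status is planned. All of this stands and limits the severity.

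A reader might infer that the 2-week prevalence is overstated, or is overstated by some number of points. The documents do not support either. They contain no rate of frequent normal stools, caretaker screening works against the error, and the literal 24-hour wording pulls the estimate the other way.

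**Conclusion.** The point holds as a fault in a stated rule. The definition counts stools without regard to consistency, so it admits children who do not have diarrhea. If every true case meets the count and the two-week window is applied, recorded prevalence exceeds true prevalence for any f above zero, so the estimate may be biased upward. The amount is unknown, and the figures above illustrate assumed rates only.

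Separately, the Case definitions contradict themselves on the period for the count and differ from the form. Applied literally, the last-24-hours phrase would miss earlier episodes.

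This is a minor to moderate wording fault on an optional secondary indicator. It does not affect the nutrition outcomes or their sample sizes.

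**What to change.** In the Case definitions and in question 10 of the Appendix 1 form, define diarrhea as three or more loose or watery stools within any 24-hour period during the prior 2 weeks. This adds the consistency criterion and removes the conflict over the time window. Carry the terms for loose and watery through translation, back-translation and pretesting, so that caretakers in each language hear the intended distinction.

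The cost is a few words in two places, with no change to sampling, specimens or, to any real extent, interview length. In the Case definitions the edit changes both the consistency criterion and the period, and should be recorded as both. Results will not be strictly comparable with earlier count-only surveys, and reports should say so. In the model above the edit brings f to zero only if caretakers report consistency correctly; some misreporting will remain.

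### The protocol defines acute lower respiratory infection as cough with fever, but the example form asks about fever with difficulty breathing and never about cough

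*Protocol*

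**What the plan says.** Objective 8 of the Protocol (section Objectives) is: "Estimate the cumulative 2-week prevalence of diarrheal disease and acute lower respiratory infection in children 6-59 months of age".

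The Case definitions section, in the paragraph on diarrhea and acute lower respiratory infection, makes this operational.

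- Respiratory: "Acute lower respiratory infection is defined as the presence of cough and fever", and a child who had this at any time in the prior 2 weeks counts as positive.
- Diarrhea: "survey workers define diarrhea as 3 or more bowel movements in the prior 24 hours". The next sentence adds: "The child's having had diarrhea at any time in the prior 2 weeks is considered positive".

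The child form in Appendix 1 has one question for each condition.

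- Question 11 asks whether, over the last two weeks, the child "had fever and difficulty" breathing. It is a single Yes/No/Unknown item.
- Question 10 asks about diarrhea over the last two weeks and explains diarrhea as at least three stools within 24 hours.

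The Data collection section presents this form as an example and says that interviewers read the questions word for word. The form's heading identifies it as that of a 2002 survey in Afghanistan.

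**The concern.** When questions are read verbatim, the wording of the question is the definition in practice. If the question names different symptoms from the case definition, the reported prevalence carries the definition's name but counts other children. No later analysis can repair this, because a symptom that was not asked about cannot be recovered.

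At stake is how one reported figure is read. A relief agency comparing it with another survey that asked about cough and fever would be comparing two conditions under one label. Because the protocol is generic and meant for reuse, one team could build its form from the Case definitions section and another could copy Appendix 1. Both would believe they were following the same protocol.

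The diarrhea definition raises a lesser question. It mentions two time spans, and the shorter one, taken alone, could be mistaken for the recall window.

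**Working it through.** The protocol states no assumed prevalence, precision or sample size for either condition. Its sample size table covers only wasting, stunting, anemia and low BMI, so there is no figure to reproduce. The check is a comparison of the texts.

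**Respiratory infection, side by side**

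| Source | Symptoms required | Window |
|---|---|---|
| Case definitions | cough and fever | 2 weeks |
| Appendix 1, question 11 | fever and difficulty breathing | 2 weeks |

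**Is cough asked elsewhere?** The child form runs from question 1 to question 31. Questions 1 to 12 go to the caretaker, 13 to 27 record the examination, and 28 to 31 are measurements and hemoglobin. None asks about cough. The list in the Variables section has no respiratory or diarrhea entry, so questions 10 and 11 are the only place in the document where objective 8 becomes data.

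**What can be derived from question 11?** Treat the symptoms as belonging to one illness, and split the children who matter into three groups, as proportions of all children:

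- a: cough, fever and difficulty breathing
- b: cough and fever, no difficulty breathing
- c: fever and difficulty breathing, no cough

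Then:

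- prevalence as defined = a + b
- prevalence as collected = a + c
- difference (defined minus collected) = (a + b) − (a + c) = b − c

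The form yields only the sum a + c. It does not separate a from c and does not observe b. The sign of b − c is therefore unknown.

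The form's result does not even bound the defined prevalence. Whatever a + c is, the value a = 0 with b = 0 is possible, which gives a defined prevalence of 0. The value c = 0 with b = 1 − a is equally possible, which gives 1. The logical range is 0% to 100%. The true gap is surely much narrower, but nothing in the documents narrows it.

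Because question 11 is one combined item, a No does not show which symptom was absent, so fever alone cannot be recovered either.

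**Diarrhea, side by side**

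| Source | Frequency | Window |
|---|---|---|
| Case definitions, first sentence | at least 3 movements in the prior 24 hours | – |
| Case definitions, next sentence | – | any time in 2 weeks |
| Objective 8 | – | 2 weeks |
| Appendix 1, question 10 | at least 3 stools in 24 hours | 2 weeks |

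Three of the four lines give the 2-week window. The 24 hours works as the frequency threshold for calling an episode diarrhea. Only the word *prior* in the first sentence conflicts with this, and the form does not use it.

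**The case against.** The strongest reply is that Appendix 1 is only an example. The protocol covers many surveys, each choosing some of the listed objectives, with questions pretested and revised locally. A mismatch with one 2002 form does not show what later surveys ask. This stands, and it limits the point: a reader might infer that objective 8 goes unmeasured throughout the programme, and the documents do not support that.

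It does not remove the point. This is the only form supplied, and it is offered as a model. The Bias section relies on translation and back-translation to make sure questions collect what they should. That safeguard cannot catch a mismatch already present in the English text. Pretesting for clarity and cultural fit would not necessarily catch it either.

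A second reply is that the outcome is ancillary: it does not enter the sample size examples, and the interventions listed in the protocol are nutritional. This also stands. No nutrition estimate is affected.

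Two further inferences are tempting and should be resisted.

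- A reader might take fever with difficulty breathing as the stricter definition and conclude that the form undercounts. The sets are not nested: question 11 also picks up children with fever and difficulty breathing but no cough, so the direction is open.
- A reader might take the diarrhea sentence to mean that only children ill in the last day count, so that the reported figure is several times too low. The next sentence, objective 8 and question 10 all contradict that reading, and the form collects no 1-day measure.

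**Conclusion.** The respiratory mismatch is real and follows from the text alone. On the form supplied, the defined condition cannot be computed, and a different symptom pair would be reported under its name. The size and direction of the error cannot be derived from the documents, because they give no symptom frequencies and the two pairs overlap only in part.

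The conclusion holds for any survey that uses question 11 as worded while reporting under the Case definitions section. It does not extend to surveys whose forms ask about cough and fever. It leaves the sample size and the anthropometric and micronutrient estimates untouched.

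For diarrhea the fault is one of wording only: the form measures the 2-week prevalence that objective 8 calls for.

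The correction should be made before the form is reused. It costs almost nothing, and it cannot be made after data collection.

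**What to change.** 1. **Reconcile the respiratory definition and question 11** so that both use the same symptoms, and name in the Case definitions section the one combination that is reported. One way is to ask whether, in the prior 2 weeks, the child had an illness with cough and then, *for that same illness*, whether there was fever and whether there was difficulty breathing. Tying the symptoms to one illness matters: separate 2-week items would count cough in one week and fever in the other as a case. This adds one question per child if only cough and fever are asked, and two if difficulty breathing is kept.

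   A cough-first sequence does not reproduce question 11, because children without cough are not asked further. If the authors intend to report fever with difficulty breathing, the alternative is to keep question 11 and change the case definition to match, with no added question.

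2. **Reword the diarrhea definition** to at least 3 bowel movements in any 24-hour period during the prior 2 weeks, in line with question 10 and objective 8. This changes one phrase in the protocol and nothing on the form.
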